The PLUNGER Stroke Trial

A comparison of cyclic manual direct aspiration thrombectomy (Plunger technique) vs. static manual direct aspiration thrombectomy for treatment of acute large vessel occlusion stroke with the Raptor Aspiration Catheter

Principle Investigator:

[name], PhD
Director of Vanderbilt Cerebrovascular Program
Associate Professor of Neurology and Neurosurgery
Vanderbilt University Medical Center
Nashville, TN

Study Summary

Title	A comparison of cyclic manual direct aspiration thrombectomy (Plunger technique) vs. static manual direct aspiration thrombectomy for treatment of acute large vessel occlusion stroke with the Raptor Aspiration Catheter
Short title	The Plunger Stroke Trial
Objective	To compare the efficacy and safety of cyclic manual direct aspiration thrombectomy (Plunger technique) vs static aspiration for direct aspiration thrombectomy with the Raptor Aspiration Catheter
Design	A randomized, controlled trial of the Plunger technique vs. static manual direct aspiration thrombectomy for treatment of acute large vessel occlusion stroke. At least one pass with aspiration is required.
Sample size	A sample size of 500 subjects will detect a 15% absolute difference in successful first pass rate between the two groups at 90% power.
Duration	With 20 sites, enrollment can be completed in one year (Sites to be decided)
Primary endpoint	First pass effect (FPE) defined as TICI 2c or 3 after the first attempt of direct aspiration thrombectomy
Safety endpoint	Rate of symptomatic intracranial hemorrhage (sICH)
Secondary endpoints	Overall rate of TICI 2b or 3 recanalization with Plunger vs. static aspiration Functional outcome at 90 days based on mRS assessment Rate of successful navigation of aspiration catheter to clot Rate of rescue treatment with stent-retrievers Rate of complete clot ingestion Recanalization rates with the two different sizes of Raptor Rate of recanalization by clot density on CT (hyperdense vs isodense)
Inclusion criteria	Acute ischemic stroke due to occlusion of the terminal ICA or M1 segment of the MCA Treatment can be initiated within 24 hours of symptom onset Age 18 years or older
Exclusion criteria	Evidence of acute intracranial hemorrhage prior to treatment Failure to obtain informed consent

Background

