The Carrier inner navigation catheter from Balt is specifically designed for use with the Raptor catheters and can be placed in the region of the carotid siphon and ophthalmic origin, allowing the catheter to easily track over it and to the clot face.

Finally, the microwire used for the triaxial navigation of a Raptor to the intracranial vasculature can also counter the difficulty of tortuous anatomy. While any 0.014" neurovascular wire may be used, the Aristotle 18 wire (Scientia Vascular) has particular advantages for this specific purpose. Though it has a diameter of 0.018", it is extremely flexible and can be used quite similarly to a typical 0.014" wire, such as the Synchro2 from Stryker.

In the PLUNGER trial the Raptor *must* be used, and it is strongly encouraged that operators utilize the Carrier inner navigation catheter and the Aristotle 18 guidewire. If initial attempts at navigation with a Raptor catheter fails, then other catheters may be used at the discretion of the operator. These will be regarded as protocol deviations and will require description of the anatomy and rationale for device choice. Guide catheter choice is left to the discretion of the operator, including the optional use of balloon guide catheters versus long guide sheaths.

Aspiration syringe and technique

Trial participants will all be treated with direct aspiration thrombectomy, an established endovascular treatment modality for acute ischemic stroke caused by large vessel occlusion. Subjects will be randomized to static aspiration or plunger aspiration, which will be delivered via standardized techniques.

The vacuum source, or 'pump,' will be the Merit Medallion VacLok syringe which is designed to apply aspiration through a catheter. The plunger is pulled back and twisted to lock the syringe in the 'open' position, thereby creating and holding a vacuum in the syringe and the catheter to which it is attached.

[figure not shown]

In direct aspiration thrombectomy, the catheter is navigated to the clot face and then a vacuum is applied by attaching the VacLok syringe and locking the syringe in the open position, as above. Typically the VacLok syringe will be attached to the open luer connector on the stopcock and rotating hemostatic valve assembly that is already attached to the catheter hub.

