For *static aspiration*, the VacLok syringe is opened to create suction on the clot for a minimum of one minute (some interventionalists may prefer a longer 'dwell time' to encourage more clot ingestion, which is fine). Once the syringe is locked open, a timer is used to ensure adequate timekeeping. Once at least 1 minute or more has passed, then the catheter is carefully withdrawn into the guide catheter and removed. The guide catheter is then thoroughly aspirated to clear any fragmented clot. The duration of aspiration will be reported on the case report form (CRF). Other syringes or devices for aspiration may be introduced during the trial at the discretion of the steering committee.

Plunger Technique

The VacLok syringe is also used for the Plunger technique. The catheter is navigated to the clot face and aspiration is applied by drawing the syringe plunger back. However, the syringe is not locked, but instead the plunger is repeatedly pulled back and then released in a cyclic fashion [[Froehler, JNIS 2023](#)]. There is no need to cycle slowly, as seen in the how-to video. Operators may wish to pull the plunger more quickly than it is released, though our *in vitro* studies have shown that there is always negative pressure at the catheter tip and therefore no risk of 'pushing' the clot. Although obvious, it is important to note that when the plunger is released it should not be actively pushed forward as this could push the clot out of the catheter and into the distal vasculature.

When using the Plunger technique in the trial, active plunging must be performed for at least 30 s at a time, with pauses of no more than 30 s. When paused, the syringe must be locked in the fully open / full vacuum position. Total aspiration time, including active plunging and static vacuum pauses, must be at least one minute (one cycle of plunging). As with static aspiration, some surgeons may prefer to use a longer total aspiration time, which is acceptable. The VacLok syringe must then be locked in the full vacuum position before the catheter is removed in a fashion identical to that described above for the static aspiration technique.

Rescue treatment

Rescue therapy may be provided to the subject at the discretion of the study investigator. In the event that aspiration thrombectomy fails to achieve successful reperfusion (defined as TICI \geq 2b) after at least one attempt, any other FDA-approved thrombectomy device may be used by the study physician.

Training

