All investigators and sub-investigators will receive training on the above techniques prior to site initiation. Training will either be in-person or via video teleconference. Additionally, each site must confirm that they stock the Raptor, VacLok syringe, and Carrier navigation catheter prior to site initiation.

Objective and endpoints

Study objective

The object of this study is to compare the efficacy and safety of the Plunger technique vs static aspiration for direct aspiration thrombectomy using the Raptor aspiration catheter.

Primary effectiveness endpoint

The primary endpoint is the first pass effect (FPE), defined as TICI 2c or 3 after the first attempt of direct aspiration thrombectomy, as determined by core lab assessment (see p. 16)

Primary safety endpoint

The primary safety endpoint is the rate of symptomatic intracranial hemorrhage (sICH) at 24 hours, as defined by 1) new intracranial hemorrhage on CT and 2) neurologic deterioration associated with worsening NIHSS by 4 or more points.

Secondary endpoints

- Overall rate of TICI 2b or 3 recanalization with Plunger technique vs. static aspiration vs. rescue therapy. At least one thrombectomy attempt with the assigned technique will be made prior to rescue treatment with a stent-retriever or other device if needed.
- Functional outcome at 90 days based on modified Rankin scale (mRS) assessment. All patients will be contacted *by phone* at 90 days to assess their functional status.

- Rate of successful navigation of aspiration catheter to clot. This will be reported by the site investigator. If the aspiration catheter cannot be navigated to the clot then rescue treatment with a stent-retriever may be used.
- Rate of rescue treatment with stent-retrievers. This rescue therapy will be employed after **at least** one attempt with aspiration thrombectomy, or if the Raptor cannot be successfully navigated to the clot.
- Rate of complete clot ingestion. Sites will report if the clot is completely ingested through the Raptor and into the syringe, or if it is partially ingested in the tip of the Raptor.
- Recanalization rates with the two different sizes of Raptor: analyses will compare recanalization of the 0.071" vs. 0.074" sizes of Raptor.

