A participant will be considered lost to follow-up for the secondary end-point, mRS, if he or she is unable to be contacted by the study site staff, either via telephone or an in-person meeting at 90-days after randomization. When all reasonable attempts to locate the subject have been exhausted, the subject will be considered lost to follow-up and their data will be excluded from the data analysis from the time of last contact onward. All data collected prior to last contact will be included in data analysis.

Statistical analysis

Sample size calculation

The true rate of successful FPE with aspiration thrombectomy can be estimated based on several prior studies. The COMPASS trial reported an 83% rate of TICI 2b or 3 after the first attempt with aspiration thrombectomy [4]. Similarly, Kang et al reported TICI 2b or 3 in 82% of patients after the first pass with aspiration thrombectomy [8], but that rate dropped to 19% when limiting the definition of successful FPE to TICI 2c or 3 [8]. Similarly, the ETIS investigators reported a 24% rate of TICI 3 FPE with the Sofia catheter [9]. Synthesizing these results, we estimate the predicted FPE (TICI 2c or 3) rate of static aspiration thrombectomy to be 25%.

While it is difficult to predict the treatment effect of the Plunger technique, our experience is that there is significantly more total clot ingestion with this technique. Total clot ingestion would be expected to particularly impact the TICI 2c/3 rate of FPE. Therefore, we estimate that the Plunger technique may increase FPE rate by 15% over static aspiration (predicted Plunger FPE of 40%).

A minimum sample size of 462 would be required to detect a difference of 15% between these two groups with 90% power at alpha of 0.05. Given that the actual FPE rates are difficult to estimate and accounting for inability to access the lesion with the Raptor and missing data, we plan for a total minimum sample size of 500.

Population for analysis

A modified intention-to-treat (mITT) analysis will be employed, wherein all subjects for whom navigation of the Raptor to the clot failed will be excluded from the subsequent ITT analyses. This is because those subjects will not be treated by either of the techniques being studied in this trial. Once navigation failures are excluded, the remainder of the population will be compared based on assigned treatment technique per randomization.

Analysis of primary effectiveness endpoint

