The primary endpoint is the first pass effect (FPE), defined as TICI 2c or 3 after the first attempt of direct aspiration thrombectomy, as determined by core lab assessment. The rate of successful FPE will be compared between the Plunger group and the static aspiration group per the mITT population as above.

Null hypothesis: the rate of successful FPE is not different between static and plunger aspiration. The rate of FPE will be compared between the two groups by chi-square analysis. If there is a significant difference between the two, then the null hypothesis will be rejected.

Analysis of primary safety endpoint

The primary safety endpoint is the rate of sICH at 24 hours compared between the static and Plunger aspiration groups. A chi-square test will assess for differences in rate of sICH between the two treatment groups in the mITT population. Secondary analyses will account for ASPECTs score and time to treatment between the two groups.

Analysis of secondary endpoints

Overall rate of TICI 2b or 3 recanalization with Plunger vs. static aspiration will also be compared using chi-square analysis on the mITT population.

For the following additional binomial secondary efficacy endpoints, treatment groups will be compared using logistic regression models as appropriate:

- Rate of successful navigation of aspiration catheter to clot
- Rate of rescue treatment with stent-retrievers
- Rate of complete clot ingestion
- Rate of recanalization by clot density on CT (hyperdense vs isodense)

The 90-day functional outcomes, including mRS and PROMIS-10, will be compared between the two groups using ordinal shift analysis.

Randomization

Patients will be randomized (1:1; permuted block randomization) once the decision is made for patient to go for thrombectomy using the REDCap randomization tool.

Adverse events

Throughout the course of the clinical investigation, all adverse events will be recorded on the applicable Adverse Event CRF. The date of onset, date of resolution, severity, and action taken will be evaluated by the Investigator. The relationship to the technique or device, relationship to the procedure, and clinical significance will be evaluated. The neurological outcomes and adverse events will be reported.

Adverse Event Classification and Definitions

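### Does naming rescue therapy in the overall TICI 2b/3 endpoint turn a two-arm comparison into a three-way one?

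*Protocol*

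**What the plan says.** The protocol describes the overall TICI 2b/3 endpoint in three places.

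- **Objective and endpoints, Secondary endpoints:** "Overall rate of TICI 2b or 3 recanalization with Plunger technique vs. static aspiration vs. rescue therapy". The sentence that follows it puts rescue after an attempt with the assigned technique, where rescue is needed.
- **Study Summary, Secondary endpoints:** "Overall rate of TICI 2b or 3 recanalization with Plunger vs. static aspiration", with no mention of rescue.
- **Analysis of secondary endpoints (within the Statistical analysis part), where the test is named:** "Overall rate of TICI 2b or 3 recanalization with Plunger vs. static aspiration will also be compared using chi-square analysis on the mITT population".

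The design text has two groups throughout. Under Aspiration syringe and technique: "Subjects will be randomized to static aspiration or plunger aspiration". The Randomization section gives a 1:1 allocation. Under Population for analysis, navigation failures are removed first ("all subjects for whom navigation of the Raptor to the clot failed will be excluded from the subsequent ITT analyses") and then "the remainder of the population will be compared based on assigned treatment technique per randomization".

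Under Rescue treatment: "Rescue therapy may be provided to the subject at the discretion of the study investigator". That section goes on to allow other devices when aspiration has not reached TICI 2b. Stent-retriever rescue is also a secondary endpoint of its own, compared between the two arms.

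**The concern.** Taken literally, the endpoint list asks for a comparison that the design cannot support, for four reasons.

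- Rescued patients already belong to the Plunger or the static arm, so the three groups overlap.
- Rescue is decided after randomisation, at the operator's discretion. It is tied largely to aspiration falling short of TICI 2b, which is this endpoint's own threshold for success. A rescue group would therefore be selected mainly on the outcome being compared.
- The mix of the two arms within that group would depend on how well each technique worked.
- The endpoint list also allows rescue after failed navigation, but those patients are outside the mITT population. The membership of a rescue group would depend on which section one followed.

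If a report placed a rescue rate beside the two arms as though it were a third treatment, a reader could take it for a comparative result. It would not be one. Endpoint wording does find its way into results tables, so the question is a fair one.

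**Working it through.** The protocol states no figure for this endpoint, so there is nothing to reproduce. The check sets the sections side by side.

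| Section | Groups named | Analysis given |
|---|---|---|
| Study Summary | 2 | none |
| Secondary endpoints | 3 (rescue added) | none |
| Aspiration syringe and technique; Randomization | 2 randomised, 1:1 | not applicable |
| Population for analysis | 2, by assignment | mITT |
| Analysis of secondary endpoints | 2 | chi-square, mITT |

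**Step 1: which text governs the analysis.** Only the last two rows say how patients are grouped and tested, and they agree with each other. An analyst working from them puts each rescued patient in the arm to which that patient was assigned and runs one two-group test. The phrase in the endpoint list does not enter that calculation, so its effect on the stated analysis is zero.

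**Step 2: whether another reading of the phrase fits.** The Angiographic core lab section calls for readings after the first pass, after the last aspiration pass and at the end of the procedure. The last two are reperfusion before and after any rescue that followed aspiration. Reporting by stage, within each arm, fits both these readings and the sentence that follows the endpoint. A third comparison group fits nothing else in the protocol.

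**Step 3: whether the choice of reading creates an error of known size or direction.** It does not. Let *p* be success after the last aspiration pass, *r* the share of failures rescued and *s* the success of rescue. If only failures are rescued, success at the end of the procedure is *p* + (1 − *p*)·*r*·*s*. As an illustration, take static *p* = 0.83. The protocol cites an "83% rate of TICI 2b or 3 after the first attempt with aspiration thrombectomy", so this is a stand-in for the rate after the last pass. Plunger *p* = 0.92, *s* = 0.8 and the values of *r* are assumptions that do not come from the protocol. The difference after the last aspiration pass is 92 − 83 = 9.0 points.

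- *r* = 0.5 in both arms: static 0.83 + 0.17 × 0.5 × 0.8 = 89.8%; Plunger 0.92 + 0.08 × 0.5 × 0.8 = 95.2%; difference 5.4 points.
- *r* = 0.2 static, 0.8 Plunger: static 0.83 + 0.17 × 0.2 × 0.8 = 85.7%; Plunger 0.92 + 0.08 × 0.8 × 0.8 = 97.1%; difference 11.4 points.

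The end-of-procedure difference can be smaller or larger than 9.0 points, depending on rescue shares that the protocol does not give. The two readings answer different questions, and neither is wrong.

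**The case for a change.** The strongest argument for a change is that the protocol itself names the comparison groups and does so inconsistently, so the mismatch cannot be put down to detail left for the SAP. The wording is that of a comparator, the reading by stage is inferred rather than stated, and deleting three words would align the sections at no cost. The same event is also listed separately as an outcome of the arms, which makes it an odd comparator to them.

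Most of this stands as a description of the text. The sections do differ, and a rescue group would not be a valid third term. What does not stand is the step to a consequence. Harm requires someone to set aside the one analysis the protocol specifies and build, from a phrase in a list, a comparison with no test, no hypothesis and no population.

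A related argument is that the protocol does not say whether the overall rate is read before or after rescue. That is a choice of estimand which a SAP may properly make, and the SAP is not at hand. The core lab collects both readings, so nothing is lost in the meantime.

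Attempts to put a size on the harm do not help either. They rest on assumed Plunger success, rescue shares and rescue success. The claim that a rescue group would have no successes before rescue holds only if failures alone are rescued, whereas the Rescue treatment section leaves rescue to discretion.

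**Conclusion.** The mismatch in wording is real, and no change to the plan follows. The specified analysis is two-arm, by assigned technique, with a chi-square test on the mITT population. Under it the effect of the extra words is zero. The primary endpoint (first-pass TICI 2c or 3), the sample size, the safety endpoint and data collection are unaffected.

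This conclusion rests on the analysis section governing the analysis, as is usual, and on the SAP, if one exists, not reintroducing rescue as a comparator. A sensible analyst would compare the two randomised arms and describe results by rescue use within each assigned arm. If the protocol is amended for other reasons, the endpoint wording can be tidied as an editorial matter.

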Patients with a large vessel occlusion who are clinically appropriate for thrombectomy will be screened for participation. Subjects who meet selection criteria below will be enrolled. Note that there are no parenchymal imaging criteria; site investigators will determine if individual patients will benefit from thrombectomy. The trial is not intended to assess clinical criteria for endovascular treatment decisions, but rather to assess *technique* of thrombectomy once that decision has been made.

Inclusion criteria

1. Acute ischemic stroke due to occlusion of the terminal ICA or M1 segment of the MCA
2. Treatment can be initiated within 24 hours of onset
3. Age of 18 years or older

Exclusion criteria

Evidence of acute intracranial hemorrhage prior to treatment

Failure to obtain informed consent

Subject withdrawal

Subjects enrolled in the study can discontinue their participation at any time for any reason without prejudice or reduction in the quality of their medical care. The investigator can terminate a subject's participation in the study to protect the subject's health. The Investigator must document this notification of withdrawal from the study in the appropriate CRF and notify the sponsor.

Data collection

Baseline data: At the time of endovascular treatment, the following data will be collected for all subjects:

- Age
- Baseline mRS
- ASPECTS score
- Hyperdense vessel sign (yes/no; site-reported)
- NIHSS
- Location of occlusion (right or left, ICA terminus or M1)

Procedure data: The following will be collected immediately after the procedure:

- Guide catheter used
- Which Raptor used (0.071" or 0.074")
- Microcatheter used (Carrier or other)
- Microwire used
- Successful navigation? (yes/no)

- Total duration of aspiration
- Total duration of plunging (if assigned to Plunger technique)
- Reperfusion (TICI) after each pass (site-assessed)
- Clot ingestion: none, partial, or complete
- Groin puncture time
- On-clot time
- Time of reperfusion
- Rescue treatment? If yes, what device and how many passes

24 hour data: To be collected at 24 hrs post-procedure +/- 6 hours:

- Imaging evidence of hemorrhage? If parenchymal, HI1, HI2, PH1, or PH2; or IVH, SAH, SDH
- Symptomatic ICH?
- NIHSS

90 day follow up: To be collected by phone at 90 days +/- 30 days

- Modified Rankin Score

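### The secondary rescue endpoint counts stent-retriever rescue only, although the protocol permits rescue with other devices, so it under-counts failures of the assigned technique

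*Protocol*

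**What the plan says.** The Rescue treatment section leaves rescue to the operator: "Rescue therapy may be provided to the subject at the discretion of the study investigator". Where aspiration has not reached TICI 2b or better after at least one attempt, "any other FDA-approved thrombectomy device may be used by the study physician". The TICI 2b/3 bullet under Secondary endpoints uses the same wide meaning. It requires an attempt with the assigned technique "prior to rescue treatment with a stent-retriever or other device if needed".

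The rescue endpoint is narrower. It reads "Rate of rescue treatment with stent-retrievers" in the Study Summary, in the Secondary endpoints list and in Analysis of secondary endpoints, where it is a binary outcome for logistic regression. The endpoint list adds that this rescue follows at least "one attempt with aspiration thrombectomy, or if the Raptor cannot be successfully navigated to the clot". Nothing in the protocol widens the count to other devices.

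The Procedure data list under Data collection has the wider field: "Rescue treatment? If yes, what device and how many passes".

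**The concern.** The trial compares two ways of aspirating through the same type of catheter. The useful question for a rescue endpoint is how often the assigned way was not enough. As worded, the endpoint answers a different question: how often a stent-retriever was taken up. A patient in whom the assigned technique failed and who was finished with, say, another aspiration system falls into the same category as a patient who needed nothing further.

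The operator performs the technique and so knows the arm, and also chooses the rescue device. The Background says that technique varies with physician preference and training, and that one operator who prefers static aspiration often uses alternatives to the 60 cc syringe. It is therefore plausible that the mix of rescue devices varies between operators. It could also vary with the technique that has just failed. If so, the comparison would mix technique failure with device preference.

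**Working it through.** **Text.** Three statements stand side by side.
- Devices allowed for rescue: any other approved thrombectomy device (Rescue treatment; the TICI 2b/3 bullet agrees).
- Devices counted by the endpoint: stent-retrievers only (Study Summary, Secondary endpoints, Analysis of secondary endpoints).
- Devices recorded: all (Procedure data).

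The set allowed is wider than the set counted, so some permitted rescues score as no rescue.

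**Size.** The protocol states no rescue rate and no device mix, so there is no figure of its own to reproduce. The inputs are:
- 250 per arm: half of the planned 500 (Sample size calculation). Navigation failures leave the modified intention-to-treat population, so this is an upper limit.
- Any-device rescue of 30% static and 20% Plunger: assumed.
- Share of rescues done without a stent-retriever, s (static) and p (Plunger): assumed and varied.
- Two-sided alpha of 0.05, unadjusted comparison of two proportions.

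Rates seen by the endpoint: static = 0.30 × (1 − s); Plunger = 0.20 × (1 − p).

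Power = Φ[(|d| − 1.96 × SE0) / SE1], where d is the difference in rates, m the mean rate, SE0 = √(2m(1 − m)/250) and SE1 = √((a(1 − a) + b(1 − b))/250) for rates a and b.

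Worked case, all devices counted: d = 0.10 and m = 0.25. SE0 = √(2 × 0.25 × 0.75/250) = 0.0387. SE1 = √((0.21 + 0.16)/250) = 0.0385. Power = Φ[(0.10 − 0.0759)/0.0385] = Φ(0.63), about 73%.

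| Non-stent-retriever share, static / Plunger | Rates seen, static vs Plunger | Power |
|---|---|---|
| 0% / 0% | 30% vs 20% | 73% |
| 10% / 10% | 27% vs 18% | 67% |
| 30% / 30% | 21% vs 14% | 54% |
| 50% / 50% | 15% vs 10% | 39% |
| 40% / 20% | 18% vs 16% | 9% |
| 50% / 10% | 15% vs 18% | direction reversed |
| 10% / 50% | 27% vs 10% | difference overstated |

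With equal shares the direction and the ratio of rates (1.5) are kept, but the absolute difference shrinks. At 30% in both arms, 250 × 0.30 × 0.30 = 22.5 static and 250 × 0.20 × 0.30 = 15 Plunger patients who were rescued count as not rescued.

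With unequal shares the outcome depends on which way they differ. The two rates are equal when 0.30 × (1 − s) = 0.20 × (1 − p), that is, when stent-retrievers make up 1.5 times as large a share of rescues under Plunger as under static. Beyond that ratio the direction reverses.

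**The case against.** The strongest reply is that nothing is misstated. One section says which devices may be used and another says which use is counted. The endpoint is worded identically in all three places. Stent-retriever rescue is a definable outcome, and the Background presents stent-retrievers as the main alternative to aspiration. A reader might infer that the protocol contradicts itself. It does not, and it never says that this endpoint is meant to capture every failure of the assigned technique. That part of the reply stands: the point concerns the choice of what to count.

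A second reply is that failure of the technique shows elsewhere. First pass effect is the primary endpoint, and the blinded core lab scores reperfusion after the first pass, after the final aspiration pass and at the end of the procedure. This holds only in part. Those scores measure reperfusion, not whether further treatment was needed. The score after the final aspiration pass is also hard to interpret when the rescue device is itself an aspiration system.

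A third reply is that no data are lost, since any rescue and its device are recorded and any-device rescue can be tabulated later. That is true, and it keeps the matter small. But the protocol fixes the narrow count, so a wider one chosen after the data are seen would be a post hoc choice between two definitions.

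Finally, counting any device does not remove operator discretion, because whether to give rescue at all is also the operator's decision. This stands as a limit of the fix.

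**Conclusion.** The endpoint under-counts failures of the assigned technique whenever a permitted device other than a stent-retriever is used for rescue. That much follows from the text. How far it under-counts is unknown, because the protocol gives neither rescue rates nor the device mix. Under the assumed 30% vs 20%, equal shares of 10% to 50% lower power from about 73% to between 67% and 39% without changing direction.

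A reader might pick out the 18% vs 16% case and conclude that the endpoint loses nearly all its power, or that it is biased against one technique. The documents support neither conclusion. That case needs shares that differ by arm in one particular way, and the opposite pattern overstates the difference. Nothing in the protocol says which pattern to expect, or that the shares will differ at all.

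This is a minor point about one secondary endpoint for which no power is stated. First pass effect is scored after the first attempt, so the primary result does not depend on it. The safety endpoint and the sample size are also untouched.

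**What to change.** Define the endpoint as rescue with any thrombectomy device or technique other than the assigned aspiration technique, compared by randomised arm. Report stent-retriever rescue as a component. State two classifications in the definition:
- crossover to the other syringe technique counts as rescue;
- how use of a non-Raptor catheter is classified, since the Navigation technique section treats it as a protocol deviation.

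The cost is a wording change in the Study Summary, Secondary endpoints and Analysis of secondary endpoints, made before data are seen. Rescue and the rescue device are already on the form. The field asks for a device, so the form instructions should say how a change of syringe technique through the same Raptor is entered. The remaining weakness is that any-device rescue is still at the unblinded operator's discretion, and the report should say so. The change affects only what is counted. No rule on when or how rescue is given is altered.
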